Experiment 2 will use a between-subjects design (see Figure 4) to study healthy volunteers. All participants will have an initial scanning session on the first day of the study where anatomical, resting-state, and DTI images will be collected. This will be followed by 1-5 days of rTMS (20-minutes per day). The number of days of rTMS will be derived from the results of Experiment 1. On the day after the last rTMS session (within 12-36 hours), a final anatomical and resting-state-scan will be collected. Immediately following each resting-state scan, we will administer the ASRQ. All participants will experience the same procedures, with the exception of the location of stimulation. Depending on group assignment, the participant will either receive stimulation to the parietal cortex, or vertex.

Contrary to Experiment 1, Experiment 2 will include behavioral testing at 3 different time points: 1) after the initial scanning session, 2) after the final scanning session, and 3) about a week after the last scanning session. This will include memory testing using the WPT-I and AMT, as well as the cognitive battery described above.

Subjects will be assigned to two groups (parietal and vertex), which will be balanced by age and sex. We will blind volunteers to stimulation type (group assignment) by recruiting participant who are naïve to the study hypothesis. Investigators scoring FC and behavioral data will be kept blind to rTMS assignment.

[figure not shown]

Figure 4. Procedures for Experiment 2. Times are estimates.

viiii. Duration of Study

Participation for healthy participants in Experiments 1 and 2 will be no more than 8 visits.

e. End of Participation

Volunteers will remain under the care of their own providers. No care will be offered to those participating in this protocol, except for any acute care required for adverse events. Findings of clinical significance, e.g., significant pathology on MRI will be shared with participants and any provider whom they designate.

5. Management of Data and Samples

i. Storage

The results of testing will be stored on password-protected computers or backed up on media stored in locked cabinets. Keys to participant identity will be stored in lab notebooks, available only to study investigators. Samples will not be stored under this protocol.

ii. Data and Sample Sharing Plan

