The following aims will be investigated using the optimal sessions determined in Specific Aim 1.

ii. Experiment 2

Specific Aim 2 (Primary Aim 1): To determine whether rTMS delivered to the parietal cortex increases parietal-hippocampal FC in healthy subjects.

For each healthy subject, the Pearson correlation coefficients (r) between time courses of BOLD activity in the parietal and hippocampal areas will be calculated to determine the functional connectivity before and after rTMS stimulation. They will be Fisher-transformed to normalize r values. *We will call this the z scores.* The change in the z scores from pre- to post- stimulation will be assessed using the one-tailed, paired *t* test.

Specific Aim 3: To measure the effects of parietal rTMS on AMT and WPT-I.

First, the change in the AMT scores from pre- to post- stimulation will be calculated. Then, the two sample *t*-tests will be used to compare the changes in the AMT scores between the parietal and the sham groups. Additionally, we will consider using the Wilcoxon rank sum tests when the changes in the AMT scores are not normally distributed in each group.

Next, we will perform a similar analysis for WPT-I scores.

Specific Aim 4: To evaluate the relationship between fMRI connectivity and AMT and WPT-I outcomes in the parietal group in healthy subjects.

For each subject, the Pearson correlation coefficients (r) between time courses of the parietal and hippocampal regions will be calculated to determine the functional connectivity before and after rTMS stimulation. Then, the changes of the z scores (Fisher transformed r values) from pre- to post- simulation will be calculated. Similarly, the changes in AMT scores from pre- to post-simulation will be computed. The linear

regression models will be used to examine the relationship between the change in functional connectivity and the change in AMT scores.

Next, we will repeat a similar analysis using WPT-I scores.

b. Power analysis

Experiment 1: The maximum number of healthy subjects for Experiment 1 is set at 15.

Experiment 2: We propose to recruit 32 healthy participants (16 subjects in each of the parietal and control groups) to participate in Experiment 2.

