We based our sample size estimate on the behavioral results from the study we are replicating (Wang et al., 2014). In Wang et al. (2014), the effect size of the memory increases caused by PPC stimulation, compared to sham stimulation, was 0.75 (Cohen's d). This was achieved using a within-subjects design. Using this effect size, to achieve a β of 0.70 using the between subjects design described in this protocol (Experiment 2), 16 participants are required.

Sixteen subjects per group also achieves sufficient power to detect FC changes. Wang et al. indicate that the mean difference in FC from post to pre stimulation in retrosplenial region was 0.1018 and its standard deviation was 0.09296. Based on their data, we assume that the mean change will be between 0.1008 and 0.1028. We also assumed its standard deviation (SD) will be between 0.085 and 0.10. A one-tailed, paired t-test was used at a significance level of 0.05. Computations were carried out using PASS (Hinze J. [2008] PASS, NCSS, LLC, Kaysville, Utah).

The following table shows estimates of power to address Primary Aim 1 given ten subjects per treatment group.

Mean of paired difference	Estimated standard deviation of the difference	Power
0.1008	0.085	0.96440
0.1018	0.085	0.96698
0.1028	0.085	0.96940
0.1008	0.093	0.93446
0.1018	0.093	0.93833

0.1028	0.093	0.94202
0.1008	0.100	0.90159
0.1018	0.100	0.90651
0.1028	0.100	0.91125

Table 1. Estimated power for primary aim 1 (N=10 in parietal group)

A sample size of ten subjects per group achieves 93.8% power to detect a mean of paired differences of 0.1018 with an estimated standard deviation of differences of 0.093 and with a significance level of 5% using a one-sided paired t-test. Under other scenarios, the estimated powers were greater than 90%.

Assuming a 50% dropout rate, we anticipate enrolling up to 101 healthy subjects (33 for Experiment 1; 64 for Experiment 2).

11. Human Subjects Protection

a. Subject selection

We will recruit healthy participants through referrals from the NIH Clinical Research Volunteer program or through self-referrals to the protocol. We will work to ensure equitable selection.

b. Justification for exclusion of subjects

i. Justification for exclusion of children

Children will not be included. The study is predicated on the work of Wang et al. (2014) who studied participants over the age of 18. Therefore, in order to replicate this result, we will recruit a sample of the same age.

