Because we intend to compare the results of Experiments 1 and 2 and because we will be attempting to replicate Wang et al. (2014), we will focus our analysis on subjects between the ages of 18-50.

ii. Justification for exclusion of subjects above the age of 50

Because neuroplasticity is reduced in older adults (Fathi, et al., 2010) including subjects above the age of 50 would reduce our power for detecting change in FC. Therefore, this group will be excluded.

iii. Justification for the exclusion of non-English speakers/readers

We are excluding non-English speakers because differences in the ability to understand the task instructions might not be apparent to us when communicating via an interpreter,

but could affect performance significantly, introducing unpredictable differences between groups of subjects.

iv. Justification for participants who have already participated in Experiment 1.

Because the persistence of the rTMS effect is unknown, participants from Experiment 1 will not be invited to participate in Experiment 2.

c. Justification for the Exclusion of other Vulnerable Subjects

i. Persons without consent capacity

Because there is a minor increment above minimal risk and no expectation of benefit, we do not feel it would be appropriate to include participants without the capacity to give informed consent.

ii. Women who are Pregnant, Plan to Become Pregnant, or are Breast-feeding

The effects of MRI on fetal development and the health of pregnant women is unknown. Therefore, women who are pregnant will be excluded and women who can become pregnant will be excluded following a positive pregnancy test.

d. Justification of sensitive procedures

This study involves no sensitive procedures.

e. Safeguards for vulnerable populations

Since the effects of rTMS and MRI on fetal development are unknown, women of childbearing potential will have a pregnancy test before each rTMS and MRI session.

i. Safeguard of vulnerable subjects (NIH employees)

Protections for employees and staff participating in this study include 1) assuring that the participation or refusal to participate will have no effect, either beneficial or adverse, on the subject's employment or position at the NIH, 2) giving employees and staff who are interested in participating the "NIH Information Sheet on Employee Research Participation" prior to obtaining consent, and 3) assuring that there will be no direct solicitation of employees or staff.

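### Free improvement: Experiment 2 balances its groups on age and sex, but the planned AMT and WPT-I comparisons ignore both, which forgoes some power if balance holds and either factor predicts change

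*Combined protocol and SAP*

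**What the plan says.** Section 4.d.viii (Experiment 2) sets the assignment rule: "Subjects will be assigned to two groups (parietal and vertex), which will be balanced by age and sex". It does not say how balance will be produced (stratified randomisation, minimisation or matching).

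Section 10.a.ii, Specific Aim 3, sets the group comparison. Change in AMT is calculated for each subject, and two-sample t-tests "will be used to compare the changes in the AMT scores between the parietal and the sham groups". I read the sham group here as the vertex group. The fallback is also unadjusted: "we will consider using the Wilcoxon rank sum tests when the changes in the AMT scores are not normally distributed in each group". For the secondary outcome the text adds: "Next, we will perform a similar analysis for WPT-I scores". No covariate, stratified or matched analysis of these comparisons appears in section 10.

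Section 10.b plans "32 healthy participants (16 subjects in each of the parietal and control groups") and takes its effect size from the study being replicated, where "the effect size of the memory increases caused by PPC stimulation, compared to sham stimulation, was 0.75" (Cohen's d). The power target is 0.70, which the text labels β.

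**The concern.** Forcing two groups to have the same age and sex distribution removes those factors from the chance variation in the group difference. An unadjusted two-sample test does not know this. It still counts the spread due to age and sex within each group as error. If either factor predicts change, the computed standard error exceeds the true one, the confidence interval is too wide, and the test rejects less often than its nominal level. The design has then paid for precision that the analysis does not collect.

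The stake is power on AMT, one of the two primary outcomes, in a comparison of 32 people planned for only 70% power.

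**Working it through.** **Inputs.** From section 10.b: 16 per group, d = 0.75, target power 0.70. The 5% one-sided level is stated there for FC. No sidedness is stated for AMT or WPT-I, so both are shown. R², the share of variance in change explained by age and sex together, is my assumption, with a range of 0 to 0.30.

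**1. The plan's sample size.** Normal approximation: n per group = 2(z₁₋α + z₀.₇₀)²/d².
- One-sided 5%: 2(1.645 + 0.524)²/0.5625 = 16.7, so 17; the exact t calculation gives 18.
- Two-sided 5%: 2(1.960 + 0.524)²/0.5625 = 21.9, so 22; exact t gives 23.

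The stated 16 is therefore close only to the one-sided calculation. Exact power at 16 per group is 66.6% one-sided and 53.7% two-sided.

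**2. Standard error under exact balance** (in units of the SD of change). The unadjusted test estimates √(2/16) = 0.354. The true value is 0.354 × √(1 − R²), which is 0.335 at R² = 0.10, 0.316 at 0.20 and 0.296 at 0.30. The overstatement is 1/√(1 − R²): 1.054, 1.118 and 1.195.

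**3. Power after adjustment, by formula.** Noncentral t on 28 degrees of freedom, with noncentrality 0.75/(0.354√(1 − R²)). This is 2.121, 2.236, 2.372 and 2.535 at R² = 0, 0.10, 0.20 and 0.30. One-sided power is 66.5%, 70.4%, 74.8% and 79.6%. Against the 66.6% in step 1, break-even is at an R² of about 0.5%.

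**4. Simulation with balance.** 15,000 trials per cell, sex 8/8 in each group, age uniform on 18–50 and matched within sex, R² split equally between age and sex, and the same age and sex effects in both arms. Each pair of figures is unadjusted / adjusted, in per cent.

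| R² | One-sided type I error | One-sided power | Two-sided power |
|---|---|---|---|
| 0 | 4.9 / 5.0 | 66.6 / 66.3 | 53.7 / 53.6 |
| 0.02 | 4.9 / 5.1 | 66.3 / 66.7 | 53.6 / 54.3 |
| 0.05 | 4.4 / 4.8 | 67.0 / 68.5 | 53.8 / 55.7 |
| 0.10 | 4.0 / 4.8 | 67.0 / 70.4 | 53.7 / 57.5 |
| 0.20 | 3.0 / 4.8 | 67.9 / 74.9 | 53.8 / 62.9 |
| 0.30 | 2.6 / 5.1 | 69.0 / 79.5 | 54.0 / 68.8 |

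Monte Carlo error on a power figure is about √(0.67 × 0.33/15,000) = 0.4 points.

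**5. Simulation without balance** (age and sex left to chance). The unadjusted one-sided type I error stays between 4.7% and 5.4%, so that standard error is valid. One-sided power, unadjusted / adjusted, is 65.9 / 63.2 at R² = 0, 66.2 / 65.3 at 0.05, 66.1 / 67.8 at 0.10 and 66.8 / 72.2 at 0.20. Adjustment costs 2.7 points at zero and starts to pay somewhere between R² = 0.05 and 0.10.

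The rank-sum fallback was not simulated. The same reasoning applies to it in direction, but the figures are for the t-test.

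**The case against.** **No evidence of the size.** The documents give no R². The outcomes are change scores in healthy adults aged 18–50, so stable differences in level by age or sex are already subtracted. A small R² is quite possible, and the gain is then small. This stands, and it is why the size is given as a range.

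**Section 11.b.ii.** A reader might infer that the protocol itself says age predicts the outcome, since it argues that "including subjects above the age of 50 would reduce our power for detecting change in FC". The documents do not support that step. The passage concerns FC, not AMT or WPT-I. It justifies excluding people over 50 and says nothing about variation within 18–50. It also describes a weaker response to stimulation, which is a different thing from age predicting change in both arms. When age was made to alter only the parietal effect (8,000 trials per cell), one-sided power was 65.6% unadjusted against 65.7% adjusted for a 25% shift in effect per SD of age, and 64.0% against 65.0% for a 50% shift. Nothing in the documents says that sex predicts change.

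**FC.** A reader might extend the point to the FC primary outcome. It does not apply there: "The change in the z scores from pre- to post- stimulation will be assessed using the one-tailed, paired" t-test. That test compares pre with post, not parietal with vertex. The hypothesis in section 2.b does compare the sites, so the absent comparison is a separate issue.

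**Balance may fail.** The method is unstated, and section 10.b assumes 50% dropout, which could undo balance among those analysed. Dropout does not strengthen the case for an overstated standard error: as balance is lost, the unadjusted standard error becomes valid and adjustment may cost a little power. This also stands.

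**Conclusion.** The point holds as an inexpensive gain in efficiency for AMT and WPT-I. It is not an error that threatens validity. Under close balance, with age and sex acting alike in both arms, adjustment gains about 3 points of one-sided power at R² = 0.10 and 7 at 0.20. The two-sided gains are about 4 and 9 points. At R² = 0.10 adjusted one-sided power reaches the plan's 70% without another participant.

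Two stronger readings should be resisted. One is that power is lost whenever age or sex predicts change. That needs balance to be achieved as well as an R² above break-even, and the documents establish neither. The other is that the planned tests could mislead. They are conservative under balance and correct without it, so false positives do not rise and the estimate is not biased. Nor is the balancing wasted under the present tests, since it still guards against chance confounding in a sample of 32.

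**What to change.** In section 10.a.ii, Specific Aim 3, state that AMT change and WPT-I change will each be analysed in a linear model containing arm, age (continuous) and sex, and that the arm coefficient and its confidence interval are the reported effect. Keep the unadjusted t-test as a sensitivity analysis. It would help to state the balancing method in section 4.d.viii and the sidedness of these tests in the same edit, because the figures above depend on both.

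The cost is one or two sentences and no new data: age is needed for eligibility, and demographics are recorded at screening (Appendix C). Residual degrees of freedom fall from 30 to 28. If R² is zero, that costs under half a point of power with close balance, and 2 to 3 points if the groups are not balanced.

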2. Study Objectives and hypotheses

The overall objective of this study is to determine whether functional connectivity can be used as a biomarker of rTMS synaptic modulation. The experiments outlined in this protocol will not be used to demonstrate the clinical effects of rTMS.

a. Aims

Experiment 1

Specific Aim 1: To determine the number of rTMS sessions required to produce a substantial change in FC between the parietal cortex and hippocampus in healthy subjects.

Experiment 2

Specific Aim 2: To determine whether rTMS delivered to the parietal cortex increases parietal-hippocampal FC in healthy subjects.

Specific Aim 3: To measure the effect of parietal rTMS on AMT and WPT-I, performance.

Specific Aim 4: To evaluate the relationship between fMRI connectivity and AMT and WPT-I outcomes after parietal rTMS in healthy subjects.

b. Hypotheses

i. Primary Hypotheses

Experiment 2: rTMS of the left parietal cortex will increase FC between the left parietal cortex and the hippocampus compared to rTMS of the vertex. rTMS of the left parietal cortex will significantly increase explicit memory compared to rTMS of the vertex.

ii. Secondary hypotheses:

Experiment 2: rTMS of the left parietal cortex will decrease FC between the left caudate (head) and parietal cortex compared to rTMS of the vertex. rTMS of the left parietal cortex will significantly decrease implicit memory compared to rTMS of the vertex.

3. Subjects

a. Description of study populations

We will study 50 healthy individuals (Experiment 1: 18; Experiment 2: 32). We are requesting up to 101 healthy volunteers as the accrual ceiling to account for dropouts and screening failures.

b. Inclusion criteria

Healthy individuals in Experiments 1 and 2.

- Age 18-50 (inclusive)
- English speaking and writing

c. Exclusion criteria

- Any current major neurological or psychiatric disorder such as (but not limited to) stroke, Parkinson disease, Alzheimer disease, schizophrenia or major depression
- History of seizure
- Medications acting on the central nervous system
- Ferromagnetic metal in the cranial cavity or eye, implanted neural stimulator, cochlear implant, or ocular foreign body
- Implanted cardiac pacemaker or auto-defibrillator or pump
- Non-removable body piercing
- Claustrophobia
- Inability to lie supine for 1 hour
- Pregnancy, nursing, or plans to become pregnant during the study.
- Members of the NINDS Behavioral Neurology Unit (BNU)
- For Experiment 2: Participation in Experiment 1

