As a negative control, identical rTMS will be delivered at the vertex in Experiments 2 and 3. We justify the use of vertex stimulation as a control over sham stimulation as follows. A major criticism of sham procedures in rTMS neuromodulation studies is that conventional sham techniques do not reproduce the sensation of real rTMS on the scalp. This confound is so significant that basic validity of crossover designs has fallen into serious question. It is the consensus in the community that a more rigorous and scientifically valid procedure is to use real rTMS over a scalp site that is not thought to be part of the targeted network. This also serves as a control for nonspecific neural effects of the stimulation on the brain and further restricts the possibility of spurious or misinterpreted positive results (Sandrini et al., 2011; Ziemann et al., 2008).

Importantly, our paradigm is based on that of Wang and colleagues (2014) who used off-target stimulation as a control condition and found no significant effects on connectivity or behavior. Using an inactive sham that failed to replicate the sensory effects of rTMS would invalidate our study as a replication and lead to other questions about the source of any effects of active stimulation on connectivity or behavior.

rTMS targets will be marked in the participant's anatomical MRI volume and located with a frameless stereotaxic system. If any experiment, for any reason, fails to produce useful individual targets, a literature-based location for the parietal cortex (Wang, et al., 2014) will be used as our location of stimulation. In each experiment, rTMS will only be delivered to the target in one hemisphere. To reduce the influence of diurnal variations in the responsiveness to neuroplasticity protocols (Sale, Ridding, & Nordstrom, 2008), we will make every effort to test subjects during the same time of day.

To allow participants the opportunity to experience rTMS at the parietal site and decide about continued participation, we will give them a “sample” before the first rTMS session. We will then ask the participant if they wish to continue the study.

For all experiments, FC and explicit/implicit memory will be measured within a week before the first rTMS session and immediately after the last rTMS session. Memory testing will be performed again 7-10 days after the last rTMS session. Experiment 1, however, will include no memory testing.

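### Experiment 2 does not state random or concealed allocation, so the between-group AMT and WPT-I comparisons are open to selection bias

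*Combined protocol and SAP*

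**What the plan says.** Section 4.d.viii sets the design: "Experiment 2 will use a between-subjects design (see Figure 4) to study healthy volunteers". On allocation it says only this: "Subjects will be assigned to two groups (parietal and vertex), which will be balanced by age and sex". The précis and the investigational plan in section 1 add that the design is between groups, and nothing more about how groups are formed.

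The same section describes two blinding measures. Volunteers are to be kept unaware of their group by recruiting people who do not know the hypothesis. For assessment: "Investigators scoring FC and behavioral data will be kept blind to rTMS assignment".

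Section 2.b.i states the primary memory hypothesis as a contrast between groups: "rTMS of the left parietal cortex will significantly increase explicit memory compared to rTMS of the vertex". Section 9.a lists AMT change as a primary outcome and section 9.b lists WPT-I change as secondary. In section 10.a.ii, Specific Aim 3, two-sample t tests "will be used to compare the changes in the AMT scores between the parietal and the sham groups", with a rank sum test as fallback and a similar analysis for WPT-I. No covariates are named. The group called sham there is the vertex group.

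FC is analysed differently under Specific Aim 2: "The change in the z scores from pre- to post- stimulation will be assessed using the one-tailed, paired" t test. Section 10.b gives the size: "We propose to recruit 32 healthy participants (16 subjects in each of the parietal and control groups").

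**The concern.** A two-sample comparison supports a causal reading only if the groups are alike apart from stimulation site. Random, concealed allocation secures this on average for all factors, measured or not. Balancing on age and sex secures it for two. The rule as written can be met by hand: staff may place each new volunteer wherever the age and sex balance allows, guided by anything else they know.

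What they know could include outcome-related data. Sections 4.d.iii and 4.d.viii place the baseline scan and memory tests before the first stimulation session, and the time of assignment is not given. At stake is whether a difference in AMT change reflects the stimulation or who was put in each group. Unlike a choice of model, allocation cannot be redone after enrolment.

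**Working it through.** **1. Search for an allocation method.** The readable text was checked for random allocation, sequence generation, minimisation, concealment, the person who assigns, and the time of assignment. None is stated. The four stated safeguards, and what each covers, are:

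- Age and sex balance: those two factors only.
- Pre-to-post change scores: stable additive baseline differences, but not differences in learning rate, practice gain or regression to the mean.
- Hypothesis-naive volunteers: expectation effects.
- Blinded scorers: detection bias.

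None governs who enters which group.

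**2. Which tests are exposed.** AMT and WPT-I are compared between groups. The FC test for Primary Aim 1 is paired within subject, and its power table in section 10.b refers to the parietal group alone. It has no vertex term, so selection between groups cannot bias it directly.

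**3. The plan's own figure.** Inputs from section 10.b: d = 0.75, 16 per group, and a target of 0.70 (written as β, read as power). Sidedness for AMT is not stated. For a two-sample t test with n per group, df = 2n − 2 = 30 and the noncentrality is d × √(n/2) = 0.75 × √8 = 2.121.

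| Test at 5% | Critical t | Power at n = 16 | n per group for 70% |
|---|---|---|---|
| One-sided | 1.697 | 66.6% | 18 |
| Two-sided | 2.042 | 53.7% | 23 |

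The planned 16 is reproduced to within two participants per group if the test is one-sided.

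**4. Effect of an assumed selection shift.** Let assignment shift the mean AMT change by b SD in favour of parietal, with no true effect. The noncentrality becomes b × √8 and the critical values stay the same.

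| b (assumed) | Noncentrality | Two-sided rejection | One-sided rejection |
|---|---|---|---|
| 0 | 0 | 5.0% | 5.0% |
| 0.2 | 0.566 | 8.5% | 13.7% |
| 0.3 | 0.849 | 13.0% | 20.7% |
| 0.5 | 1.414 | 27.8% | 39.6% |

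**5. Precision gained by adjusting for age and sex.** If these factors explain a share R² of the variance in AMT change, the effective effect size is 0.75 / √(1 − R²). This ignores the two degrees of freedom spent on covariates, which cost about 0.2 percentage points.

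| R² (assumed) | Effective d | Two-sided power |
|---|---|---|
| 0 | 0.750 | 53.7% |
| 0.02 | 0.758 | 54.5% |
| 0.05 | 0.769 | 55.8% |
| 0.10 | 0.791 | 58.1% |
| 0.20 | 0.839 | 63.1% |

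**6. Sample size after the fix.** Randomising changes no planned number: 16 per group, 32 in total, and 32 / (1 − 0.5) = 64 enrolled at the plan's 50% dropout.

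**The case against.** The strongest reply is that silence is not proof. Assignment with balance on age and sex is compatible with stratified randomisation or minimisation, and the Experiment 2 figures are not available, although the Figure 4 caption points to procedures and timing. This stands: a reader might infer that the groups will not be randomised, and the documents do not support that. They leave it open. But a plan that hand allocation would satisfy still needs to say which is meant.

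Other strong readings also fail:

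- **No protection at all.** Age and sex balance and change scores give some. Motivation or memory ability matters only so far as it affects change.
- **Only scorers are blinded.** Section 4.d.viii also plans to blind volunteers. That staff delivering stimulation know the site is a reasonable inference, not a statement in the plan.
- **The FC result is biased too.** The planned FC test makes no group comparison. That it does not test the FC hypothesis against vertex is a separate matter; a between-group FC test, if added, would share this exposure.
- **Withdrawals after the trial stimulation bias the groups.** Section 4.d.iii offers it "To allow participants the opportunity to experience rTMS at the parietal site and decide about continued participation", with no difference by group described. If volunteers are blind as planned, withdrawal at that step should not differ by arm.
- **The next assignment is predictable.** No algorithm is given, so this cannot be shown.

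It is also fair to say that the size of the shift is unknown, and that leaving balanced covariates out of the model costs precision but does not create selection bias.

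**Conclusion.** The concern holds for AMT and WPT-I. The allocation rule, followed as written, lets staff choose groups, and the stated safeguards protect only partly. One of the two primary outcomes of Experiment 2 rests on that comparison.

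The size is conditional. Assumed shifts of 0.2 to 0.5 SD give a two-sided false-positive rate of 8.5% to 27.8%, against a nominal 5%. No document gives a shift, so these figures show what selection would do if present, not that it is likely. The gain from adjustment likewise depends on an assumed R². It takes two-sided power at d = 0.75 from 54% to about 55–56% if R² is 2–5%, or 58–63% if it is 10–20%. Adjustment is a secondary benefit; the main need is a stated, concealed random method.

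**What to change.** Replace the allocation sentence in section 4.d.viii with text to this effect: participants are randomised 1:1 to parietal or vertex by a computer-generated method, stratified or minimised on sex and age band with a random element; if blocks are used, their sizes vary; the allocation stays concealed until eligibility is confirmed, baseline measures are complete, and the participant has had the sample and chosen to continue. Name the role that holds the sequence.

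In section 10.a.ii, include sex and age in the between-group models for AMT and WPT-I, and analyse participants in the group to which they were allocated.

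This is Version H and Experiment 1 is marked completed, so some Experiment 2 participants may already be allocated. If so, apply the new method to the remainder, report how the earlier participants were assigned, and describe the comparison for them as non-randomised.

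The cost is a protocol paragraph, a sequence and two model terms, with no extra participants or visits. The downsides are small: exact age balance may be slightly looser than by hand, and with 32 participants some blocks may be incomplete.
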